2.2 Benefits and Risks to Subjects

Preclinical toxicology studies of ABBV-105 in animals and ex vivo human samples suggest that the potential risks to human subjects of ABBV-105 treatment are anemia, bleeding associated with platelet dysfunction, and lymphopenia. Reductions in lymphocytes and the known mechanism of action suggest the potential for an increased susceptibility to infection.

In Phase 1 Studies M16-356 (single doses of ABBV-105 ranging from 2 to 125 mg), M16-357 (multiple doses of ABBV-105 ranging from 3 - 60 mg), and M16-044 (co-administration of upadacitinib 30 mg with ABBV-105 ranging from 10 - 60 mg), ABBV-105 alone or ABBV-105 co-administration with upadacitinib was well-tolerated with no serious adverse events (SAEs) observed in healthy adult subjects.

Taken together, the safety data from the Phase 1 program support further development of ABBV-105 given alone or in combination with upadacitinib (ABBV-599) in Phase 2 in subjects with RA.

For safety monitoring, the following are included in the protocol:

- Exclusion of subjects with chronic or recent infections;
- Screen subjects for tuberculosis (TB); exclude patients with active TB or latent TB without
 history of appropriate prophylaxis: latent TB as assessed by Interferon Gamma Release Assay
 (IGRA) QuantiFERON Tuberculosis (TB) Gold in Tube Test or equivalent (i.e., or T SPOT.*TB* test; as
 available and if compliant with local TB guidelines) and/or a purified protein derivative (PPD)
 test (or both if required per local guidelines).
- Subjects will also be screened for human immunodeficiency virus (HIV) and hepatitis B and C.
- If a subject develops a serious infection or opportunistic infection with study treatment, study drug should be interrupted and appropriate treatment of the infection should be initiated.
- Review SAEs of infection on a real time basis and query for additional information as clinically indicated
- A supplemental herpes zoster form will be used to collect additional information for any herpes zoster infections.

See Section 3.4 for information on the Data Monitoring Committee (DMC).

For further details, please see findings from completed studies, including safety data in the ABBV-105 and upadacitinib Investigator's Brochures.^{7,8}

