Table 3. AEs Requiring Supplemental Reports

Adverse Event	Supplemental Report
Cardiac events Myocardial infarction or unstable angina Heart failure Cerebral vascular accident and transient ischemic attack Cardiovascular procedures (SAE Supplemental Procedure eCRF)	MACE eCRF
Discontinuation or interruption of study drug due to a hepatic-related AE A hepatic-related SAE ALT/AST > 8 × ULN or ALT/AST > 3 × ULN with a total bilirubin > 2 × ULN	Hepatic AE eCRF
Renal impairment Renal dysfunction Renal failure Serum creatinine > 2.0 mg/dL	Renal eCRF
Herpes zoster infection	Herpes zoster eCRF
Thrombotic events Non-cardiac, non-central nervous system (CNS) embolic or thrombotic event (i.e., deep vein thrombosis or pulmonary embolism)	Embolic and Thrombotic (non-cardiac, non-CNS) eCRF

If an AE meets any of the following criteria, it is to be reported to AbbVie as an SAE within 24 hours of the site being made aware of the SAE:

Death of Subject	An event that results in the death of a subject.
Life-Threatening	An event that, in the opinion of the investigator, would have resulted in immediate fatality if medical intervention had not been taken. This does not include an event that would have been fatal if it had occurred in a more severe form.
Hospitalization or Prolongation of Hospitalization	An event that results in an admission to the hospital for any length of time or prolongs the subject's hospital stay. This does not include an emergency room visit or admission to an outpatient facility.
Congenital Anomaly	An anomaly detected at or after birth, or any anomaly that results in fetal loss.
Persistent or Significant Disability/Incapacity	An event that results in a condition that substantially interferes with the activities of daily living of a study subject. Disability is not intended to include experiences of relatively minor medical significance such as headache, nausea, vomiting, diarrhea, influenza, and accidental trauma (e.g., sprained ankle).

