Important Medical Event Requiring Medical or Surgical Intervention to Prevent Serious Outcome An important medical event that may not be immediately lifethreatening or result in death or hospitalization, but based on medical judgment may jeopardize the subject and may require medical or surgical intervention to prevent any of the outcomes listed above (i.e., death of subject, life threatening, hospitalization, prolongation of hospitalization, congenital anomaly, or persistent or significant disability/incapacity). Additionally, any elective or spontaneous abortion or stillbirth is considered an important medical event. Examples of such events include allergic bronchospasm requiring intensive treatment in an emergency room or at home, blood dyscrasias or convulsions that do not result in inpatient hospitalization, or the development of drug dependency or drug abuse.

All AEs reported from the time of study drug administration until 30 days after discontinuation of study drug administration will be collected, whether solicited or spontaneously reported by the subject. In addition, SAEs and protocol-related nonserious AEs will be collected from the time the subject signs the study-specific informed consent.

AbbVie will be responsible for Suspected Unexpected Serious Adverse Reactions (SUSAR) reporting for the Investigational Medicinal Product (IMP) in accordance with global and local requirements.

AEs will be monitored throughout the study to identify any of special interest that may indicate a trend or risk to subjects.

Adverse Events of Special Interest

The following adverse events of special interest (AESI) will be monitored during the study:

- Serious infections
- Opportunistic infections
- Herpes zoster
- Tuberculosis
- Malignancy (all types)
- Gastrointestinal perforations
- Adjudicated cardiovascular events (e.g., major adverse cardiovascular event [MACE])
- Anemia
- Neutropenia
- Lymphopenia
- Increased serum creatinine and renal dysfunction
- Hepatic events and increased hepatic transaminases
- Elevated creatine phosphokinase (CPK)

• Embolic and thrombotic events (non-cardiac, non-CNS).

Adverse Event Severity and Relationship to Study Drug

The investigator will classify AEs according to the Rheumatology Common Toxicity Criteria v.2.0 (Appendix F).

If no grading criteria are provided for the reported event, then the event should be as follows:

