## Appendix B. Definition of Adverse Events of Special Interest

Adverse Events of Special Interest (AESI) will be identified using the following search criteria:

AESI	Type of MedDRA Query	Broad or Narrow Search	SMQ/CMQ Search Criteria
Serious Infections	CMQ		"Infections" – Subset for SAEs
Opportunistic Infection	CMQ		"Opportunistic Infection"
Possible Malignancy	SMQ	Narrow	"Malignancies"
Malignancy	SMQ		"Malignant tumours"
Non-Melanoma Skin Cancer (NMSC)	SMQ	Broad	Skin Malignant tumours (Broad SMQ) removing Melanoma CMQ
Malignancy excluding NMSC			"Malignant tumours" SMQ removing NMSC output
Lymphoma	SMQ		"Malignant Lymphomas"
Hepatic Disorder (Hepatic Events and Increased Hepatic Transaminases)	SMQ	Narrow	"Drug Related Hepatic Disorders"
Gastrointestinal Perforations	SMQ	Narrow	"Gastrointestinal Perforation"
Anemia	CMQ		"Non-Hemolytic and Non-Aplastic Anemias"
Neutropenia	CMQ		"Hematological Toxicity – Neutropenia"
Lymphopenia	CMQ		"Hematological Toxicity – Lymphopenia (Veliparib Product Specific)"
Herpes Zoster	CMQ		"Herpes Zoster"
Creatine Phosphokinase (CPK) Elevation	PT		Search only for the PT of "Blood creatine phosphokinase increased"
Renal Dysfunction	SMQ	Narrow	"Acute Renal, Failure"
Tuberculosis	CMQ		"Tuberculosis"
Adjudicated Cardiovascular Events	Output from CAC		

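### SAP Appendix B states no search for the increased-creatinine half of the protocol's renal adverse event of special interest

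*SAP*

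**What the plan says.** Protocol 6.1 gives the list of AESIs to be monitored. One item has two parts, "Increased serum creatinine and renal dysfunction"; another is anemia, with no type excluded. Protocol 6.1, Table 3, requires a supplemental renal form for renal impairment, dysfunction or failure, and also for "Serum creatinine > 2.0 mg/dL" on its own.

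SAP 9.2.6 identifies the AESI categories by the MedDRA searches in Appendix B. In that table:

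- The renal row is titled Renal Dysfunction, is a standardised query with narrow scope, and is specified as "Acute Renal, Failure".
- The CPK row is a preferred-term search for "Blood creatine phosphokinase increased".
- The hepatic row carries "Hepatic Events and Increased Hepatic Transaminases" in its title and uses a narrow standardised query.
- The anemia row uses a company query named "Non-Hemolytic and Non-Aplastic Anemias".

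The AESI categories feed three kinds of output: the overview with between-group differences and 95% CIs (SAP 9.2.2), the summaries by system organ class and preferred term (9.2.6), and the subject listing (9.2.11).

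**The concern.** The protocol names a laboratory rise as part of an AESI. The SAP table that decides who is counted has neither a label nor a search term for it. Protocol 6.1 defines an adverse event so as to include an abnormal laboratory finding, so a creatinine increase can be reported without any diagnosis of renal failure. Whether such a report reaches the AESI outputs then depends on the contents of a query labelled acute renal failure and run at narrow scope.

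At stake is the completeness of the renal AESI results by arm. These outputs carry the between-group difference with its interval and the subject-level listing, and a reader would look there for a renal signal. Sites would also complete supplemental renal forms for events that the AESI analysis is not specified to find.

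**Working it through.** No figure in the plan can be reproduced here. The check is a comparison of definitions.

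**Step 1: the renal item, part by part.**

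| Protocol 6.1 | SAP Appendix B label | SAP Appendix B search |
|---|---|---|
| Increased serum creatinine | none | none stated |
| Renal dysfunction | Renal Dysfunction | narrow acute renal failure query |

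The first part has no counterpart in the label or in the search. The second part keeps its label, and its search is named for a narrower condition.

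**Step 2: how the same table treats other laboratory AESIs.** For CPK elevation Appendix B names the laboratory preferred term. For the hepatic item it keeps the transaminase wording in the title but gives no separate laboratory term. For creatinine it does neither.

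**Step 3: is the gap closed elsewhere in the SAP?** SAP 9.2.2, 9.2.6 and 9.2.11 add no further search, and no section explains a deliberate narrowing. The version history says that the AESI table was updated in version 3.0 to agree with the protocol, so agreement was the aim.

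**Step 4: where a creatinine rise is still counted.**

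- SAP 9.2.3 tabulates all treatment-emergent events by preferred term and treatment group.
- SAP 9.3 grades creatinine by NCI CTC, gives shift tables from baseline to the maximum category, and counts and lists subjects meeting PCS criteria.
- Table C-1, row L11, starts Grade 2 above 1.5 times baseline. Protocol 6.2, Table 4, names a rise above 1.5 times baseline that is also above the ULN, so the laboratory analysis reaches rises of that size whether or not an adverse event was reported.

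The possible loss is therefore confined to the AESI outputs.

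**Step 5: anemia.** The protocol item is unrestricted, while the query's name sets aside two types. Protocol 2.2 says that "the potential risks to human subjects of ABBV-105 treatment are anemia, bleeding associated with platelet dysfunction, and lymphopenia", without distinguishing types of anemia. The query's terms are not in the documents, so the name is the only evidence. Hemoglobin falls of any cause are graded in Table C-1, row K1.

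**The case against.** The strongest reply is that the contents of both queries are unknown. The hepatic row shows that a standardised query may be meant to cover a laboratory rise without its own preferred term, so the absence of a creatinine term does not prove that such events go uncounted. This stands, and it is why the conclusion says that events may be left out. It does not remove the point: the hepatic row at least keeps the laboratory wording in its title, and the renal row does not.

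A second reply is that creatinine is fully analysed from laboratory values and that all adverse events appear by preferred term. This also stands. A reader might infer that creatinine events vanish from the safety reporting; SAP 9.2.3 and 9.3 show that they do not.

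A third reply is that the AESI outputs are descriptive and enter no hypothesis test, and that choosing searches is the SAP's job. That is true and limits the weight of the point. Still, the SAP should either implement the protocol's named category or say why it does not.

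A fourth reply is that putting a laboratory term into an acute renal failure category would mix mild rises with organ failure. This is right, and it shapes the fix.

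**Conclusion.** The point holds for the renal item. Appendix B, followed as written, states no search for increased serum creatinine, a named part of a protocol AESI. Creatinine increases reported as adverse events without renal failure may be missing from the AESI overview, risk differences, summaries and listing.

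The size cannot be put as a number of subjects. The documents give no rate of creatinine increases and no term list for the query, and any count would be a guess. The effect is on which events enter certain descriptive safety tables. It touches no efficacy result, significance level or data collection.

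The conclusion assumes that the narrow query does not already contain a creatinine-increase term; this must be checked in the MedDRA version used. If it does, what remains is a mismatch in labels.

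The anemia item is secondary and minor. A reader might infer from the query's name that hemolytic and aplastic cases are certainly excluded from the AESI. The documents do not show the terms, so they support a request to check and no more. Such cases would in any event appear in the tables by preferred term.

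**What to change.** In Appendix B, add a separate row for increased serum creatinine with a preferred-term search, for example Blood creatinine increased, in the style of the CPK row. Keep the acute renal failure query as its own row so that laboratory rises and organ failure are reported apart. If the narrower definition was intended, say so and give the reason.

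Check the terms of the anemia query. If hemolytic and aplastic anemia are excluded, show them on a second line under the anemia AESI.

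The cost is one row, possibly a second line, and the matching search code. The AESI tables will contain more non-serious laboratory terms. No visit, assessment or data collection changes.

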#### Appendix C. Potentially Clinically Significant Criteria for Safety Endpoints

The criteria for Potentially Clinically Important (PCS) laboratory findings are determined by OMERACT criteria in Table C-1, and the PCS criteria for vital sign findings are described in Table C-2.

#### Table C-1.OMERACT Criteria

Rheumatology Common Toxicity Criteria v.2.0 Based on Woodworth TG, et al. Standardizing assessment of adverse effects in rheumatology clinical trials II. Status of OMERACT Drug Safety Working Group May 2006: OMERACT 8. Standardizing Assessment and Reporting of Adverse Effects in Rheumatology Clinical Trials: Enabling Description of Comparative Safety Profiles for Antirheumatic Therapies (Note that for L9. CPK and L11. Creatinine, the criteria in this table is replaced by the NCI CTC grade, as the NCI CTC grade is used for analysis for these two parameters.)					
	1 – Mild Asymptomatic, or transient Short duration (< 1 week) No change in life style No medication or OTC	2 – Moderate Symptomatic Duration (1 – 2 weeks) Alter lifestyle occasionally Meds relieve. (may be prescription), Study drug continued	3 – Severe Prolonged symptoms, reversible, major functional impairment Prescription meds/partial relief May be hospitalized < 24 hr Temporary study drug discontinuation, or/and dose reduced	4 – Includes Life Threatening At risk of death Substantial disability, especially if permanent. Multiple meds Hospitalized > 24 hr Study drug discontinued	
A. Allergic/Immun	ologic				
A1. Allergic reaction/ hypersensitivity (includes drug fever)	Transient rash: drug fever < 38°C: transient, asymptomatic bronchospasm	Generalised urticaria responsive to meds; or drug fever > 38°C, or reversible bronchospasm	Symptomatic bronchospasm requiring meds; symptomatic urticaria persisting with meds, allergy related oedema/angioedema	Anaphylaxis, laryngeal/pharyngeal oedema, requiring resuscitation	
A2. Autoimmune reaction	Seriologic or other evidence of autoimmune reaction, but patient asymptomatic: all organ function normal and no treatment is required (e.g., vitiligo)	Evidence of autoimmune reaction involving a non-essential organ or functions, requiring treatment other than immunosuppressive drugs (e.g., hypothyroidism)	Reversible autoimmune reaction involving function of a major organ or toxicity requiring short term immunosuppressive treatment (e.g., transient colitis or anaemia)	Causes major organ dysfunction, or progressive, not reversible, or requires long-term administration of high dose immunosuppressive therapy	

A3. Rhinitis	Transient, non-	Prescription med.	Corticosteroids or other	NA
(includes sneezing, nasal stuffiness, post-nasal discharge)	prescription meds relieve	required, slow	prescription med. with persistent disabling symptoms such as impaired exercise tolerance	
A4. Serum sickness	Transient, non- prescription meds relieve	Symptomatic, slow response to meds (e.g., oral corticosteroids)	Prolonged; symptoms only partially relieved by meds; parenteral corticosteroids required	Major organ dysfunction, requires long-term high-dose immunosuppressive therapy
A5. Vasculitis	Localised, not requiring treatment; or rapid response to meds; cutaneous	Symptomatic, slow response to meds (e.g., oral corticosteroids)	Generalised, parenteral corticosteroids required or/and short duration hospitalisation	Prolonged, hospitalisation, ischemic changes, amputation
B. Cardiac				
B1. Arrhythmia	Transient, asymptomatic	Transient, but symptomatic or recurrent, responds to meds	Recurrent/persistent; maintenance prescription	Unstable, hospitalisation required, parenteral meds
B2. Cardiac function decreased	Asymptomatic decline in resting ejection fraction by > 10%, but < 20% of baseline value	Asymptomatic decline of resting ejection fraction $\geq 20\%$ of baseline value	CHF responsive to treatment	Severe or refractory CHF
B3. Edema	Asymptomatic (e.g., 1 + feet/ calves), self- limited, no therapy required	Symptomatic (e.g., 2 + feet/ calves), requires therapy	Symptoms limiting function (e.g., 3 + feet/ calves, 2 + thighs), partial relief with treatment prolonged	Anasarca; no response to treatment
B4. Hypertension (new onset or worsening)	Asymptomatic, transient increase by > 20 mmHg (diastolic) or to > 150/100 if previously normal, no therapy required	Recurrent or persistent increase > 150/100 or by > 10 mmHg (diastolic), requiring and responding readily to treatment	Symptomatic increase > 150/100, > 20 mmHg, persistent, requiring multi agency therapy, difficult to control	Hypertensive crisis
B5. Hypotension (without underlying diagnosis)	Transient, intermittent, asymptomatic, orthostatic decrease in blood pressure > 20 mmHg	Symptomatic, without interference with function, recurrent or persistent > 20 mmHg decrease, responds to treatment	Syncope or symptomatic, interferes with function, requiring therapy and sustained medical attention, dose adjustment or drug discontinuation	Shock

B6. Myocardial ischaemia	Transient chest pain/ECG changes; rapid relief with nitro	Recurring chest pain, transient ECG ST-T changes; treatment relieves	Angina with infarction, no or minimal functional compromise, reduce dose or discontinue study drug	Acute myocardial infarction, arrthymia or/and CHF
B7. Pericarditis/ pericardial effusion	Rub heard, asymptomatic	Detectable effusion by echocardiogram, symptomatic NSAID required	Detectable on chest x- ray, dyspnoea; or pericardiocentesis; requires corticosteroids	Pulsus alternates with low cardiac output; requires surgery
B8. Phlebitis/ thrombosis/ Embolism (excludes injection sites)	Asymptomatic, superficial, transient, local, or no treatment required	Symptomatic, recurrent, deep vein thrombosis, no anticoagulant therapy required	Deep vein thrombosis requiring anticoagulant therapy	Pulmonary embolism
C. General (constit	utional)			
C1. Fatigue/malaise (asthenia)	Increase over baseline; most usual daily functions maintained, short term	Limits daily function intermittently over time	Interferes with basic ADL, persistent	Unable to care for self, bed or wheelchair bound > 50% of day debilitating, hospitalisation
C2. Fever (pyrexia) (note: fever due to drug allergy should be coded as allergy)	Transient, few symptoms 37.7 – 38.5°C	Symptomatic, recurrent 38.6 – 39.9°C. Relieved by meds	$\geq$ 40°C; $\leq$ 24 h, persistent symptoms; partial response to meds	$\geq$ 40°C, debilitating, > 24 h, hospitalisation; no relief with meds
C3. Headache	Transient or intermittent, no meds or relieved with OTC	Persistent, recurring, non-narcotic analgesics relieve	Prolonged with limited response to narcotic medicine	Intractable, debilitating, requires parenteral meds
C4. Insomnia	Difficulty sleeping, short term, no interfering with function	Difficulty sleeping interfering with function, use of prescription med	Prolonged symptoms, with limited response to narcotic meds	Debilitating, hospitalisation; no relief with meds
C5. Rigors, chills	Asymptomatic, transient, no meds, or non-narcotic meds relieve	Symptomatic, narcotic meds relieve	Prolonged symptoms, with limited response to narcotic meds	Debilitating, hospitalisation; no relief with meds
C6. Sweating (diaphoresis)	Episodic, transient	Frequent, short term	Frequent, drenching, disabling	Dehydration, requiring IV fluids/hospitalization > 24 hrs
C7. Weight gain	5% -9.9%	10% - 19.9%	20% - 30%	NA
C8. Weight loss	5%-9.9%	10% - 19.9%	20% - 30%	NA

D. Dermatologic				
D1. Alopecia	Subjective, transient	Objective, fully reversible	Patchy, wig used, partly reversible	Complete, or irreversible even if patchy
D2. Bullous eruption	Localised, asymptomatic	Localised, symptomatic, requiring treatment	Generalised, responsive to treatment; reversible	Prolonged, generalised, or requiring hospitalisation for treatment
D3. Dry skin	Asymptomatic, controlled with emollients	tomatic, Symptoms Generali and with eventually with AD nts (1 – 2 wks) persister controlled with emollients treatment		Disabling for extended period, unresponsive to ancillary therapy and requiring study drug discontinuation for relief
D4. Injection site reaction	Local erythema, pain, pruritis, < few days	Erythema, pain, oedema, may include superficial phlebitis, 1 – 2 wks	Prolonged induration, superficial ulceration; includes thrombosis	Major ulceration necrosis requiring surgery
D5. Petechiae (without vasculitis)	Few, transient asymptomatic	Dependent areas, persistent up to 2 wks	Generalised, responsive to treatment; reversible	Prolonged, irreversible, disabling
D6. Photosensitivity	Transient erythema	Painful erythema and oedema requiring topical treatment	Blistering or desquamation, requires systematic corticosteroids	Generalised exfoliation or hospitalisation
D7. Pruritis	Localised, asymptomatic, transient, local treatment	Intense, or generalised, relieved by systematic medication	Intense or generalised; poorly controlled despite treatment	Disabling, irreversible
D8. Rash (not bullous)	Erythema, scattered macular/popular eruption; pruritis transient; TOC or no meds	Diffuse macular/popular eruption or erythema with pruritus; dry desquamation; treatment required	Generalised, moist desquamation, requires systemic corticosteroids; responsive to treatment; reversible	Exfoliative or ulcerating; or requires hospitalisation; or parenteral corticosteroids
D9. Induration/fibrosis/ Thickening (not sclerodermal)	Localized, high density on palpation, reversible, no effect on ADL and not disfiguring	Local areas < 50% body surface, not disfiguring, transient interference with ADL, reversible	Generalized, disfiguring, interferes with ADL, reversible	Disabling, irreversible, systemic symptoms

E. Ear/Nose/Throa	t			
E1. Hearing loss	Transient, intermittent, no interference with function	Symptomatic, treatment required, reversible	Interferes with function; incomplete response to treatment	Irreversible deafness
E2. Sense of smell	Slightly altered	Markedly altered	Complete loss, reversible	Complete loss, without recovery
E3. Stomatitis	Asymptomatic	Painful, multiple, can eat	Interferes with nutrition, slowly reversible	Requires enteral support; residual dysfunction
E4. Taste disturbance (dysgeusia)	Transiently altered; metallic	Persistently altered; limited effect on eating	Disabling, effect on nutrition	NA
E5. Tinnitus	Intermittent, transient, no interference with function	Requires treatment, reversible	Disabling, or associated with hearing loss	Irreversible deafness
E6. Voice changes (includes hoarseness, loss of voice, laryngitis)	Intermittent hoarseness, able to vocalise	Persistent hoarseness, able to vocalise	Whispered speech, slow return of ability to vocalise	Unable to vocalize for extended
E7. Xerostomia (dry mouth)	Transient dryness	Relief with meds	Interferes with nutrition, slowly reversible	Extended duration interference with nutrition, requires parenteral nutrition
F. Eye/Ophthalmo	logic			
F1. Cataract	Asymptomatic, no change in vision, non-progressive	Symptomatic, partial visual loss, progressive	Symptoms impairing function, vision loss requiring treatment, including surgery	NA
F2. Conjunctivitis	Asymptomatic, transient, rapid response to treatment	Symptomatic, responds to treatment, changes not interfering with function	Symptoms prolonged, partial response to treatment, interferes with function	NA
F3. Lacrimation increased (tearing, watery eyes)	Symptoms not requiring treatment, transient	Symptomatic, treatment required, reversible	Unresponsive to treatment with major effect on function	NA
F4. Retinopathy	Asymptomatic, non-progressive, no treatment	Reversible change in vision; readily responsive to treatment	Disabling change in vision ophthalmological findings reversible, sight improves over time	Loss of sight

F5. Vision changes (e.g., blurred, photophobia, night blindness, vitreous floaters)	Asymptomatic, transient, no treatment required	Symptomatic, vision changes not interfering with function, reversible	Symptomatic, vision changes interfering with function	Loss of sight
F6. Xerophtalmia (dry eyes)	Mild scratchiness	Symptomatic without interfering with function, requires artificial tears	Interferes with vision/function, corneal ulceration	Loss of sight
G. Gastrointestinal	l			
G1. Anorexia	Adequate food intake, minimal weight loss	Symptoms requiring oral nutritional supplementation	Prolonged, requiring iv support	Requires hospitalization for nutritional support
G2. Constipation	Asymptomatic, transient, responds to stool softener, OTC laxatives	Symptomatic, requiring prescription laxatives, reversible	Obstipation requiring medical intervention	Bowel obstruction. Surgery required
G3. Diarrhea	Transient, increase of 2 – 3 stools/day over pre-treatment (no blood or mucus), OTC agents relieve	Symptomatic, increase 4 – 6 stools/day, nocturnal stools, cramping, requires treatment with prescription meds	Increase > 6 stools/day, associated with disabling symptoms, e.g., incontinence, severe cramping, partial response to treatment	Prolonged, dehydration, unresponsive to treatment, requires hospitalization
G4. Dyspepsia (heartburn)	Transient, intermittent, responds to OTC antacids, H-2 blockers	Prolonged, recurrent, requires prescription meds, relieved by meds	Persistent despite treatment, interferes with function, associated with GI bleeding	NA
G5. GI bleed (gastritis, gastric or duodenal ulcer diagnosed-define aetiology)	Asymptomatic, endoscopic finding, haemocult + stools, no transfusion, responds rapidly to treatment	Symptomatic, transfusion ≤ 2 units needed; responds to treatment	Haematemesis, transfusion 3 – 4 units, prolonged interference with function	Recurrent, transfusion > 4 units, perforation, requiring surgery, hospitalisation
G6. Haematochezia (rectal bleeding)	Haemorrhodial, asymptomatic, no transfusion	Symptomatic, transfusion $\leq 2$ units, reversible	Recurrent, transfusion > 3 – 4 units	> 4 units, hypotension, requiring hospitalization

G7. Hepatitis	Laboratory abnormalities, asymptomatic, reversible	Symptomatic laboratory abnormalities, not interfering with function, slowly reversible	Laboratory abnormalities persistent > 2 wks, symptoms interfere with function	Progressive, hepato- renal, anasarca, pre- coma or coma
G8. Nausea, or nausea/vomiting (use diagnostic term)	Transient, intermittent, minimal interference with intake, rapid response to meds	Persistent, recurrent, requires prescription meds, intake maintained	Prolonged, interferes with daily function and nutritional intake, periodic iv fluids	Hypotensive, hospitalization, parenteral nutrition, unresponsive to out- patient management
G9. Pancreatitis	Anylase elevation, intermittent nausea/vomiting, transient, responds rapidly to treatment	Amylase elevation with abdominal pain, nausea, occasional vomiting, responsive to treatment	Severe, persistent abdominal pain with pancreatitic enzyme elevation, incomplete or slow response to treatment	Complicated by shock, haemorrhage (acute circulatory failure)
G10. Proctitis	Perianal pruritus, haemorrhoids (new onset), transient, or intermittent, relieved by OTC meds	Tenesmus or ulcerations, anal fissure, responsive to treatment, minimal interference with function	Unresponsive to treatment, marked interference with function	Mucosal necrosis with haemorrhage, infection, surgery required
H. Musculoskeleta	l			
H1. Avascular necrosis	Asymptomatic MRI changes, non-progressive	MRI changes and symptoms responsive to rest and analgesia	MRI changes, symptoms requiring surgical intervention	Wheelchair bound; surgical repair not possible
H2. Arthralgia	Intermittent transient symptoms, no meds or relieved by OTC meds	Persistent or recurrent symptoms, resolve with meds, little effect on function	Severe symptoms despite meds impairs function	Debilitating, hospitalisation required for treatment
H3. Leg cramps	Transient, intermittent, does not interfere with function	Recurrent symptoms, minimally interferes with function or sleep, responds to meds	Persistent, prolonged interference with function or sleep, partial or no response to meds	NA
H4. Myalgia	Occasional; does not interfere with function	Frequent, requires meds (non-narcotic); minor effects on function	Major change in function/lifestyle, narcotic pain meds	Debilitating, profound weakness, requires wheelchair, unresponsive to meds

I. Neuropsychiatrie	c				
I1. Anxiety or Depression (mood alteration)	Symptomatic, does not interfere with function; no meds	Frequent symptoms, responds to meds; interferes with ADL at times	Persistent, prolonged symptoms, partial or no response to meds, limits daily function	Suicidal ideation or danger to self	
I2. Cerebrovascular ischaemia	NA	Single transient ischaemic event, responsive to treatment	Single transient ischaemic event, responsive to treatment		
I3. Cognitive disturbance	Subjective symptoms, transient, intermittent, not interfering with function	ive Objective Persistent, or worsening objective symptoms, it, persisting, interferes with daily function ing with occasionally occasionally			
I4. Depressed consciousness (somnolence)	Observed, transient, intermittent, not interfering with function	Somnolence or sedation, interfering with function	Persistent, progressive, obundation, stupor	Coma	
I5. Inability to concentrate	Subjective symptoms, does not interfere with function	Objective findings, interferes with function	Persistent, prolonged objective findings or organic cause	NA	
I6. Insomnia (in absence of pain)	Occasional difficulty sleeping, transient intermittent, not interfering with function	Recurrent difficulty sleeping; requires meds for relief; occasional interference with function	Persistent or worsening difficulty sleeping; severely interferes with routine daily function	NA	
I7. Libido decreased	Decrease in interest	Loss of interest; influences relationship	Persistent, prolonged interfering with relationship	NA	
I8. Peripheral motor neuropathy	Subjective or transient loss of deep tendon reflexes; function maintained	Objective weakness, persistent, no significant impairment of daily function	Objective weakness with substantial impairment of function	Paralysis	
I9. Peripheral sensory neuropathy (sensory disturbance)	InamainedFunctionSubjectiveObjective sensorysymptoms withoutloss, persistent, notobjective findings,interfering withtransient, notfunction		Prolonged sensory loss or paraethesias interfering with function	NA	

r				
I10. Seizure	NA	Recurrence of old seizures, controlled with adjustment of medication	Recurrence/ exacerbation with partial response to medication	Recurrence not controlled, requiring hospitalization; new seizures
I11. Vertigo (dizziness)	Subjective symptoms, transient, intermittent, no treatment	Objective findings, recurrent, meds relieve, occasionally interfering with function	Persistent, prolonged, interfering with daily function; partial response to medication	Debilitating without response to medication, hospitalization
J. Pulmonary				
J1. Asthma	Occasional wheeze, no interference with activitiesWheezing, requires oral meds, occasional interference with function		Debilitating, requires nasal O 2	Requires ventilator assistance
J2. Cough	Transient, intermittent, occasional OTC meds relieve	Persistent, requires narcotic or other prescription meds for relief	Recurrent, persistent coughing spasms without consistent relief by meds, interferes with function	Interferes with oxygenation; debilitating
J3. Dyspnea	Subjective, transient, no interference with function	Symptomatic, intermittent or recurring, interferes with exertional activities	Symptomatic during daily routine activities, interferes with function, treatment with intermittent nasal O 2 relieves	Symptomatic at rest, debilitating, requires constant nasal O 2
J4. Pleuritic pain (pleurisy)	Transient, intermittent symptoms, no treatment or OTC meds relieve	Persistent symptoms, requires prescription meds for relief	Prolonged symptoms, interferes with function, requires frequent narcotic pain relief	Debilitation, requiring hospitalisation
J5. Pneumonitis (pulmonary infiltrates)	Asymptomatic radiographic changes, transient, no treatment required	Symptomatic, persistent, requiring corticosteroids	Symptomatic, requiring treatment including O 2	Debilitating, not reversible; or requiring assisted ventilation
J6. Pulmonary function decreased (FVC or carbon monoxide diffusion capacity – DLCO)	76% – 90% of pre- treatment value	51% – 75% of pre- treatment value	26% – 50% of pre- treatment value	$\leq 25\%$ of pre- treatment value

Laboratory Data					
K. Haematology					
K1. Hgb (g/dl) decrease from pre-treatment	1.0 - 1.4	1.5 - 2.0	2.1 – 2.9, or Hgb < 8.0, > 7.0	$\geq$ 3.0; or Hgb < 7.0	
K2. Leukopenia (total WBC) × 1000	3.0 - 3.9	2.0 - 2.9	1.0 - 1.9	< 1.0	
K3. Neutropenia (× 1000)	1.5 – 1.9	1.0 - 1.4	0.5 - 0.9	< 0.5	
K4. Lymphopenia (× 1000)	1.5 – 1.9	1.0 - 1.4	0.5 - 0.9	< 0.5	
K5. Platelets (× 1000)	75 – LLN	50 - 74.9	20 – 49.9; platelet transfusion required	< 20; recurrent platelet transfusions	
L. Chemistry					
L1. Hypercalcaemia (mg/dl)	1.1 × ULN – 11.5	11.6 - 12.5	12.6 – 13.5; or symptoms present	> 13.5; or associated coma	
L2. Hyperglycemia (mg/dl) Fasting	140 - 160	161 – 250	251 - 500	> 500, or associated with ketoacidosis	
L3. Hyperkalaemia (mmol/l)***	5.5 - 5.9	6.0 - 6.4	6.5 – 7.0 or any ECG change	> 7.0 or any arrhythmia	
L5. Hypocalcaemia (mg/dl)	0.9 × LLN – 7.8	7.7 – 7.0	6.9 – 6.5; or associated with symptoms	< 6.5 or occurrence of tetany	
L6. Hypoglycemia (mg/dl)	55 – 64 (no symptoms)	40 – 54 (or symptoms present)	30 – 39 (symptoms impair function)	< 30 or coma	
L7. Hyponatraemia (mmol/l)***	-	125 – 129	120 – 124	< 120	
L8. Hypokalaemia (mg/dl)***	-	3.0 - 3.4	2.5 - 2.9	< 2.5	
L9. CPK (also if polymyositis-disease)****	> ULN – 1.5 × ULN	$> 2.5 - 5.0 \times ULN$ $> 5.0 - 10.0 \times ULN$		> 10.0 × ULN	
L10. Serum uric acid	1.2 – 1.6 × ULN	$1.7 - 2.9 \times \text{ULN}$	$3.0 - 5.0 \times ULN$ or gout	NA	
L11. Creatinine (mg/dl)****	> 1 – 1.5 × Baseline; > ULN – 1.5 × ULN	> 1.5 - 3.0 × Baseline; > 1.5 - 3.0 × ULN	> 3.0 baseline; > 3.0 - 6.0 × ULN	> 6.0 × ULN	

L12. SGOT (AST)	1.2 – 1.5 × ULN	1.6 – 3.0 × ULN	$3.1 - 8.0 \times ULN$	> 8.0 × ULN	
L13. SGPT (ALT)	$1.2 - 1.5 \times ULN$	$1.6 - 3.0 \times ULN$	3.0 - 8.0  imes ULN	> 8.0 × ULN	
L14. Alkaline phosphatase	1.1 – 1.5** × ULN	1.6 – 3.0 × ULN	3.0 – 5.0 × ULN	> 5.0 × ULN	
L15. T. bilirubin	1.1 - 1.4  imes ULN	$1.5 - 1.9 \times ULN$	2.0 - 3.0  imes ULN	> 3.0 × ULN	
L16. LDH	1.3 - 2.4  imes ULN	2.5-5.0  imes ULN	5.1 - 10  imes ULN	$> 10 \times ULN$	
M. Urinalysis					
M1. Haematuria	Micro only	Gross, no clots	Clots, transfusion < 2 units	Transfusion required	
M2. Proteinuria (per 24 h)	300 – 500 mg (tr/1 +)	501 – 1999 mg (2 +)	2 – 5.0 g (3 +) nephrotic syndrome	5.0 g (4 +) anasarca	
M3. WBC in urine	NA	NA	Indicating acute interstitial nephritis	Associated with acute renal failure	
M4. Uric acid crystals	Present without symptoms	NA	With stones or symptoms of stones (e.g., renal colic)	Causing renal outflow obstruction and hospitalization	

\*: in L11,  $1.5 - 1.8 \times ULN$  is changed to  $1.4 - 1.8 \times ULN$ .

\*\*: in L14,  $1.1 - 2.0 \times ULN$  is changed to  $1.1 - 1.5 \times ULN$ .

in L3, L7 and L8, mg/dl is changed to mmol/l. \*\*\*.

\*\*\*\*. NCI CTC grade.

